**Updated and Finalized Statistical
Analysis Plan of the ‘PROtective
Ventilation with Higher Versus Lower
PEEP During One–lung Ventilation
for THORacic Surgery’ (PROTHOR)
Randomized Clinical Trial**

The PROTHOR–investigators

INTRODUCTION

The 'PROtective Ventilation with High versus Low PEEP during One-lung Ventilation for THORacic surgery' (PROTHOR) randomized clinical trial compares an intraoperative ventilation strategy with higher positive end-expiratory pressure (PEEP) with recruitment maneuvers ('higher PEEP') to a conventional strategy consisting of lower PEEP of 5 cmH₂O without recruitment maneuvers ('lower PEEP'), both with low tidal volumes.¹ The primary objective of this study is to determine whether 'higher PEEP' is superior to 'lower PEEP' with regard to the incidence of postoperative pulmonary complications (PPC). Enrollment of patients in the PROTHOR study is progressing well and the study is planned to enroll the last patient in the second trimester of 2024.

To prevent outcome reporting bias and data-driven analysis results, the International Conference on Harmonization of Good Clinical Practice (ICH-GCP) recommends that clinical trials should be analyzed according to a pre-specified detailed Statistical Analysis Plan (SAP). This document presents the updated and finalized SAP of the PROTHOR study.

METHODS

Design, ethics and registration

The PROTHOR study is an international, multicenter, parallel, two–group, prospective, randomized, patient and outcome–assessor blinded superiority clinical trial designed to determine if an intra–operative higher PEEP strategy is superior to a lower PEEP strategy with respect to the development of PPC in adult patients submitted to thoracic surgery requiring one–lung ventilation (OLV).

The protocol, with a detailed description of the study population, the two strategies and follow–up plan of the PROTHOR trial were previously published elsewhere.¹ The PROTHOR study is registered at clinicaltrials.gov (study identifier NCT02963025) and was approved by the Ethical Committee of the Istanbul University, Medical Faculty, Turkey (2016/483, April 8, 2016). Additionally, the institutional review board at the University Hospital Dresden, Technische Universität Dresden, Dresden, Germany, approved the study on 23.09.2016 (reference no. EK 392092016). The respective review boards of participating sites approved the study as well.

Randomization and blinding

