Per-protocol analysis

The per-protocol population will consist of patients truly ventilated according to the protocol. Thus, patients will be excluded from this population if receiving PEEP < 10 cm H₂O in the ‘higher PEEP’ group or PEEP > 5 cm H₂O and FiO₂ < 1.0 in the ‘lower PEEP’ group, unless rescue for hypoxemia or hypercapnia required adjustments of PEEP and FiO₂ as defined by the protocol.

Subgroup analysis

Treatment effects on incidence of PPC will be analyzed according to the following predefined subgroups: 1) type of surgery (non-thoracoscopic versus thoracoscopic); 2) positioning (lateral decubitus versus supine position); 3) baseline SpO₂ < 96% versus SpO₂ ≥ 96%; 4) chronic obstructive pulmonary disease (COPD) versus non-COPD; 5) body mass index < 30 kg/m² versus ≥ 30 kg/m²; and 6) duration of one-lung ventilation < 120 versus ≥ 120 minutes. Analyses of heterogeneity of effects across subgroups will be performed with the

use of treatment-by-subgroup term added to the primary model and will be presented in a forest plot.

Other exploratory analyses

Given that the primary outcome of the present study is a collapsed composite, the choice of the statistical method is an important part of designing since various methods provide different power, depending on the situation. In addition to the standard analysis described above, the following analyses will be performed:

- Count analysis: the number of positive component events (i.e., 'count') across the composite will be assessed. The groups will be compared on the count using a Wilcoxon rank sum test, and the odds ratio with the 95% confidence interval will be assessed with a cumulative logistic regression model;
- Individual component analysis: the effect of the intervention in each component will be analyzed estimating the risk ratio and confidence intervals with Wald's likelihood ratio approximation test using a Bonferroni correction for multiple comparisons. The 99.6% Bonferroni-corrected confidence intervals will be reported ($1 - 0.05/14 = 0.996$);
- Common effect test: A multivariate (i.e., multiple outcomes per subject) generalized estimating equations (GEE) model will be used to estimate a common effect odds ratio across the components;

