Table 2 – Ventilation and Intraoperative Characteristics

	Higher PEEP (n =)	Lower PEEP (n =)	Absolute Difference (95% CI)	p value
Recruitment maneuver – no. (%)				
Number of recruitment maneuvers				
Tidal volume, mL/kg PBW				
Induction				
Final position with two lung ventilation				
10 minutes after one lung ventilation				
End of surgery, supine, two lung ventilation				
PEEP, cmH ₂ O				
Induction				
Final position with two lung ventilation				
10 minutes after one lung ventilation				
End of surgery, supine, two lung ventilation				
Peak pressure, cmH ₂ O				
Induction				
Final position with two lung ventilation				
10 minutes after one lung ventilation				
End of surgery, supine, two lung ventilation				
Plateau pressure, cmH ₂ O				
Induction				
Final position with two lung ventilation				
10 minutes after one lung ventilation				
End of surgery, supine, two lung ventilation				
Driving pressure, cmH ₂ O				
Induction				
Final position with two lung ventilation				
10 minutes after one lung ventilation				
End of surgery, supine, two lung ventilation				
Respiratory rate, breaths/min				
Induction				
Final position with two lung ventilation				
10 minutes after one lung ventilation				
End of surgery, supine, two lung ventilation				
FiO ₂				
Induction				
Final position with two lung ventilation				
10 minutes after one lung ventilation				
End of surgery, supine, two lung ventilation				
SpO ₂ , %				
Induction				
Final position with two lung ventilation				
10 minutes after one lung ventilation				
End of surgery, supine, two lung ventilation				

Table 2 – Ventilation and Intraoperative Characteristics

	Higher PEEP (n =)	Lower PEEP (n =)	Absolute Difference (95% CI)	p value
etCO ₂ , mmHg				
Induction				
Final position with two lung ventilation				
10 minutes after one lung ventilation				
End of surgery, supine, two lung ventilation				
Mean arterial pressure, mmHg				
Induction				
Final position with two lung ventilation				
10 minutes after one lung ventilation				
End of surgery, supine, two lung ventilation				
Duration of anesthesia, min				
Duration of one lung ventilation, min				
Duration of two lung ventilation, min				
Duration of surgery, min				
Duration of surgery ≥ 180 min – no. (%)				
Fluids				
Total intake, mL				
Fluid balance, mL				

Data are median (quartile 25th - quartile 75th) or N / total (%).

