	Higher PEEP (n =)	Lower PEEP (n =)	Absolute Difference (95% CI)	p value
Analgesia				
Alfentanil – no. (%)				
Dose, mg				
Fentanyl – no. (%)				
Dose, mg				
Remifentanil – no. (%)				
Dose, mg				
Sufentanil – no. (%)				
Dose, mg				
Morphine – no. (%)				
Dose, mg				
Ketamine – no. (%)				
Dose, mg				
Volatiles				
Desflurane – no. (%)				
Dose, vol%*min				
Sevoflurane – no. (%)				
Dose, vol%*min				
Sedatives				
Dexmedetomidine – no. (%)				
Dose, mg				
Midazolam – no. (%)				
Dose, mg				
Propofol – no. (%)				
Dose, mg				
Thiopental – no. (%)				
Dose, mg				
Neuromuscular blocking agents				
Atracurium – no. (%)				
Dose, mg				
Cisatracurium – no. (%)				
Dose, mg				
Rocuronium – no. (%)				
Dose, mg				
Succinylcholine – no. (%)				
Dose, mg				
Vecuronium – no. (%)				
Dose, mg				
Fluids				
Hydroxyethyl starch – no. (%)				
Dose, mL				
Gelatine – no. (%)				

eTable 4 – Intraoperative Fluid and Drug Therapy

	Higher PEEP (n =)	Lower PEEP (n =)	Absolute Difference (95% CI)	p value
Dose, mL				
Crystalloids – no. (%)				
Dose, mL				
Albumin – no. (%)				
Dose, mL				
Vasopressors				
Ephedrine – no. (%)				
Dose, mg				
Adrenaline – no. (%)				
Dose, mg				
Noradrenaline – no. (%)				
Dose, mg				
Phenylephrine – no. (%)				
Dose, mg				
Blood products				
Packed red blood cells – no. (%)				
Dose, mL				
Fresh frozen plasma – no. (%)				
Dose, mL				
Platelets – no. (%)				
Dose, mL				

Data are median (quartile 25th - quartile 75th) or N / total (%).

Abbreviations: PEEP is positive end-expiratory pressure.

eTable 5 – Protocol Deviations

	Higher PEEP (n =)	Lower PEEP (n =)	p value
Any protocol deviation – no. (%)			
SBP < 90mmHg unresponsive to fluids and/or vasoactive drugs			
New arrhythmias unresponsive to intervention (according to ACLS)			
Dosage of vasoactive drugs at the tolerance limit of the physician			
Need for massive transfusion			
Life-threatening surgical complication*			
Hypoxemia rescue**			
Hypercapnia rescue***			
Deviation from prescribed PEEP			
Deviation from tidal volume			
Other			

Data are median (quartile 25th - quartile 75th) or N / total (%).

Abbreviations: PEEP is positive end-expiratory pressure.

* Injury to the hemodynamic and respiratory system and brain, including major bleeding, tension pneumothorax, intracranial injury.

** Other than prescribed was necessary due to prolonged SpO₂ < 90%.

*** Other than prescribed was necessary due to respiratory acidosis pH < 7.20

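### The per-protocol set is defined by PEEP and FiO₂ alone, although recruitment maneuvers are part of what separates the two arms

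*SAP*

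**What the plan says.** The Introduction defines the experimental strategy as "higher positive end-expiratory pressure (PEEP) with recruitment maneuvers" and the control as "lower PEEP of 5 cmH₂O without recruitment maneuvers". Low tidal volume applies to both arms.

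The Per-protocol analysis section opens: "The per-protocol population will consist of patients truly ventilated according to the protocol". It then turns this into a rule. In one arm, "patients will be excluded from this population if receiving PEEP < 10 cm H₂O in the ‘higher PEEP’ group"; in the other, the trigger is "PEEP > 5 cm H₂O and FiO₂ < 1.0 in the ‘lower PEEP’ group". One exemption follows: "unless rescue for hypoxemia or hypercapnia required adjustments of PEEP and FiO₂ as defined by the protocol". No other section adds a criterion.

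The relevant items are planned for reporting. Proposed Table 2 (Ventilation and Intraoperative Characteristics) has rows for any recruitment maneuver and for "Number of recruitment maneuvers", and shows tidal volume at four time points. eTable 5 (Protocol Deviations) has a row for "Deviation from tidal volume". It has no row for a deviation on recruitment maneuvers.

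The Statistical analyses section describes the per-protocol analysis as additional to intention-to-treat.

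**The concern.** The label of the set and the rule that builds it do not match. The label promises patients ventilated as the protocol requires. The rule checks one of the two elements that distinguish the arms (PEEP), adds FiO₂ in one arm, and leaves the other distinguishing element (recruitment maneuvers) unchecked. The SAP would also list a patient as a tidal-volume deviator in eTable 5 while counting the same patient as adherent here.

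At stake is what the per-protocol estimate means. A reader would take it as the effect among patients who received the assigned strategy. As built, it is the effect among patients who met a PEEP and FiO₂ test. If the maneuvers carry part of the effect and adherence to them was imperfect, the two differ, and a neutral per-protocol result would say less about the complete strategy than its label suggests.

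**Working it through.** **Step 1: strategy against rule.**

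| Element | Role in the Introduction | Tested in the per-protocol rule? |
|---|---|---|
| PEEP level | Separates the arms | Yes, both arms |
| Recruitment maneuvers | Separate the arms (with / without) | No |
| Low tidal volume | Common to both arms | No |
| FiO₂ | Not part of the contrast stated there | Lower-PEEP arm only |

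**Step 2: apply the rule to three patients.**

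- Higher-PEEP arm, PEEP 10 cmH₂O or more, no recruitment maneuver: not excluded.
- Lower-PEEP arm, PEEP 5 cmH₂O, FiO₂ 1.0, recruitment maneuvers given outside rescue: not excluded. This patient meets neither lower-arm condition, so it does not matter whether both are needed to trigger exclusion.
- Either arm, PEEP and FiO₂ within the rule, tidal-volume deviation recorded: not excluded.

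The first two lack, or received, something that distinguishes the arms. The third departs from a requirement shared by both arms.

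**Step 3: the exemption.** It names adjustments of PEEP and FiO₂ only, so it does not say how a maneuver or a tidal-volume change made as rescue should be classed. eTable 5 has rows for hypoxemia and hypercapnia rescue, but no shell links an individual maneuver to a rescue episode. Whether the database can do so is not shown.

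**Step 4: what dilution could look like (illustration only).** The design difference reproduces: 23% − 17.25% = 5.75 points, and 5.75/23 = 25% relative reduction, as the Sample size section states. Everything below is assumed.

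Let s be the share of the 5.75 points due to the maneuvers, x the share of retained higher-PEEP patients without them, and y the share of retained lower-PEEP patients with them. Assume the components add and that non-adherence is unrelated to prognosis. Then:

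- higher-arm rate = 23 − 5.75(1 − sx)
- lower-arm rate = 23 − 5.75sy
- difference = 5.75 × (1 − s(x + y))

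| s | x | y | Difference (points) |
|---|---|---|---|
| 0.25 | 5% | 5% | 5.75 × 0.975 = 5.61 |
| 0.50 | 10% | 0% | 5.75 × 0.95 = 5.46 |
| 0.50 | 10% | 10% | 5.75 × 0.90 = 5.18 |
| 0.50 | 20% | 20% | 5.75 × 0.80 = 4.60 |
| 0.75 | 20% | 20% | 5.75 × 0.70 = 4.03 |

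The result ranges from almost no change to a 30% loss, depending entirely on the inputs. With s = 0, or x = y = 0, there is no dilution.

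**The case against.** **The analysis is supplementary.** This is a superiority trial with an intention-to-treat primary analysis, and the proposed table list gives the per-protocol result no table of its own. This stands and limits the importance of the point.

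**Readers can judge adherence themselves.** Proposed Table 2 and eTable 5 will show maneuvers, tidal volume and deviations by arm. This lowers the risk of misreading but does not change who is in the set.

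**Tidal volume does not separate the arms.** This is correct. A reader might infer that a tidal-volume deviation is crossover. The SAP makes low tidal volume common to both arms, so the dilution argument does not reach it. It remains a deviation that the SAP itself records, and so conflicts with the label of the set.

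**No crossover has been shown.** A reader might infer from the recruitment-maneuver rows that the plan knowingly leaves in patients who crossed over. The tables are empty shells: they show what will be reported, not what happened.

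**The bias need not be toward no difference.** The formula needs non-adherence to be unrelated to prognosis, which is doubtful in a set formed after randomization. For example, lower-PEEP patients given maneuvers may be those who were oxygenating poorly. This also stands. Dilution is one plausible mechanism, not an established net effect.

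**More exclusions bring more selection.** This is true, and is a cost of the fix. It does not justify a label that the rule does not meet.

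**Conclusion.** The mismatch holds and rests on the text alone: the stated rule classes as adherent patients who lacked, or were given, an element that separates the arms. It is a rule that misclassifies, not merely a missing detail, and is worth correcting before database lock.

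Its numerical effect is unknown. The SAP gives no figure for adherence to recruitment maneuvers or for their share of the effect, and the direction of the net bias is not assured. The tabulated differences show only how the answer moves with assumed inputs; a reader should not take the 30% loss as an estimate. Nor does the SAP support the inference that the trial's main conclusion is at risk: only the interpretation of the per-protocol analysis is affected.

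**What to change.** Before database lock, reconcile the Per-protocol analysis section with the Introduction:

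1. Add exclusions for higher-PEEP patients with no recruitment maneuver recorded, and for lower-PEEP patients with maneuvers not given as protocol-defined rescue. Take what counts as adherence from the protocol; no new clinical rule is proposed here.
2. Treat tidal-volume deviations recorded for eTable 5 as non-adherence in either arm.
3. State explicitly whether the rescue exemption extends to recruitment maneuvers and tidal volume.
4. Check whether the database separates rescue from non-rescue maneuvers. If it does not, rename the set PEEP/FiO₂-adherent and drop the statement that its members were ventilated as the protocol requires.
5. Report the number excluded by each criterion in each arm.

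The cost is SAP wording and programming on items already planned for reporting, apart from the check in item 4. The downside is a smaller set, a slightly wider interval and some further post-randomization selection; the counts in item 5 let readers see how much is removed from each arm.

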models with binomial distribution and an identity link for binary variables (reported as difference in percentages). Plots comparing ventilatory variables and vital signs among the groups during the first three hours of surgery and in the last hour will be drawn (presenting the data as mean and 95% confidence interval in each time point).

Other daily characteristics

Daily variables will be reported according to the description in **Proposed Inserts**. Absolute differences between groups will be calculated using median regression for continuous variables (reported as median difference) and generalized linear models with binomial distribution and an identity link for binary variables (reported as difference in percentages). Plots comparing daily variables among the groups will be constructed (presenting the data as mean and 95% confidence interval in each time point).

Primary outcome

The effect of 'higher PEEP' compared to 'lower PEEP' on the incidence of PPC will be assessed using a mixed-effect generalized linear model with binomial distribution and identity link, with sites included as random effects to account for the clustering effect and reported as absolute difference with a two-sided 95% confidence interval. Results will be presented in a table of outcomes (**Proposed Inserts**).

Secondary outcomes

For binary outcomes, the effect of 'higher PEEP' compared to 'lower PEEP' will be assessed using a mixed-effect generalized linear model with binomial distribution and identity link, with sites included as random effects to account for the clustering effect and reported as absolute difference with a two-sided 95%

confidence interval. For continuous outcomes, the comparison will be made using a mixed-effect median regression with sites also including as clustering effect, and reported as median difference with a two-sided 95% confidence interval. 90-day mortality will be assessed using Kaplan–Meier curves, and hazard ratios with 95% confidence intervals will be calculated with (shared-frailty) Cox proportional hazard models without adjustment for covariates and including sites as frailty. The proportional hazard assumptions will be tested using scaled Schoenfeld residuals and alternative parametric survival models will be used if the proportionality assumption is not sustained. In addition, a Holm–Bonferroni correction to control the family-wide error rate to the p values for all secondary outcomes will be done and presented in a Table.

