Gastrointestinal failure	Any type of gastrointestinal bleeding or gastrointestinal failure score documented as follows: 
• 0 = normal gastrointestinal function;• 1 = enteral feeding with under 50% of calculated needs or no feeding 3 days after abdominal surgery;• 2 = food intolerance or intraabdominal hypertension;• 3 = food intolerance and intra-abdominal hypertension; and• 4 = abdominal compartment syndrome
Number of hospital-free days at day 28	Defined as the number of days that a patient was not in hospital nor rehabilitation or nursing facility at day 28 after randomization. Hospital readmission is only counted if the patient stays overnight (= 2 days). Patients who die or have longer length of stay than 28 days are assigned zero hospital free days.

* ARDS Definition Task Force, Ranieri VM, Rubenfeld GD, et al. Acute respiratory distress syndrome: the Berlin Definition. JAMA 2012;307:2526-33.

Table 2 – Z-statistic Boundaries and Boundary Crossing Probabilities

Look	Information Fraction	N	Cumulative α spent	Cumulative β spent	Z-efficacy/harm	Z-futility	Boundary crossing probabilities under H_1	
							Efficacy	Futility
1	0.20	452	0.001	0.008	± 3.252	± 0.031	0.042	0.008
2	0.40	904	0.004	0.019	± 2.986	± 0.152	0.170	0.011
3	0.60	1355	0.009	0.036	± 2.692	± 0.631	0.281	0.017
4	0.80	1807	0.022	0.062	± 2.374	± 1.344	0.263	0.026
5	1.00	2259	0.050	0.100	± 2.025	± 2.025	0.143	0.038

Values were calculated using power = 0.90, alpha = 0.05, gamma spending function - 4 for the alpha and - 2 for the beta, expected incidence of postoperative pulmonary complications of 23% and 17.25% in the lower and higher positive end-expiratory pressure groups, respectively. Number of patients (N) is shown without correcting for dropouts. Look, interim analysis; H1, hypothesis 1 (group difference exists).

[figure not shown]
Table 3 – List of proposed tables and figures

	Description
Main paper	
Table 1	Baseline Characteristics of the Included Patients
Table 2	Ventilation and Intraoperative Characteristics
Table 3	Primary and Secondary Outcomes
Figure 1	Participant Flow Diagram

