Time-to-event analyses for PPC	Kaplan–Meier curves will be used to report time to postoperative pulmonary complications, and hazard ratios with a 95% confidence interval will be calculated with Cox proportional hazard models without adjustment for covariates.	No time-to-event analysis planned to be performed for PPC.
Time-to-event analyses for 90-day mortality	Hazard ratios with 95% confidence intervals will be calculated with Cox proportional hazard models without adjustment for covariates and including sites as frailty.	Hazard ratios with 95% confidence intervals will be calculated with (shared-frailty) Cox proportional hazard models without adjustment for covariates and including sites as frailty.
Subgroup analysis (definition)	---	Added two additional subgroups: body mass index and duration of one-lung ventilation.
Subgroup analysis (method)	The effects on subgroups will be evaluated according to the interaction effects between each subgroup and the study arms by generalized linear models and presented in a forest plot.	Analyses of heterogeneity of effects across subgroups will be performed with the use of treatment-by-subgroup term added to the primary model and will be presented in a forest plot.

LIST OF PROPOSED INSERTS

Table 1 – Baseline Characteristics of the Included Patients

	Higher PEEP (n =)	Lower PEEP (n =)
Age, years		
Age ≥ 65 years – no. (%)		
Female gender – no. (%)		
Body mass index, kg/m ²		
Body mass index ≥ 30 kg/m ²		
ARISCAT score		
ARISCAT ≥ 45 – no. (%)		
ASA physical status– no. (%)		
1		
2		
3		
4		
Priority of surgery – no. (%)		
Elective		
Urgent		
Emergency		
Surgical procedure – no. (%)		
Thoracoscopic		
Open		
Converted from thoracoscopic to open		
Cumulated ambulation score		
Co-existing disorders – no. (%)		
Hypertension		
Heart failure		
Coronary artery disease		
Diabetes		
Obstructive sleep apnea		
Chronic obstructive pulmonary disease		
Use of noninvasive ventilation		
Active cancer		
Respiratory infection within last month		
Smoking status		
Never		
Former (cessation > 3 months)		
Current		
Alcohol (> 2 drinks/day)		
Preoperative signs		
SpO ₂ , %		
Respiratory rate, breaths/min		
Heart rate, beats per minute		
Mean arterial blood pressure, mmHg		

Data are median (quartile 25th - quartile 75th) or N / total (%).

Abbreviations: PEEP is positive end-expiratory pressure; ARISCAT is The Assess Respiratory Risk in Surgical Patients in Catalonia; ASA is American Society of Anesthesiology; SpO₂ is pulse oximetry.

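### BMI and baseline SpO2 are tested as effect modifiers only through a single cut each, which loses power if the effect of higher PEEP changes gradually; a test on the recorded scale should be added.

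*SAP*

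**What the plan says.** The Subgroup analysis section of the SAP lists six subgroups for the primary outcome. Two are formed by cutting a continuous baseline measure: "body mass index < 30 kg/m² versus ≥ 30 kg/m²" and "baseline SpO₂ < 96% versus SpO₂ ≥ 96" (per cent). Heterogeneity is assessed by "use of treatment-by-subgroup term added to the primary model and will be presented in a forest plot". The primary model, under Primary outcome, is a "mixed-effect generalized linear model with binomial distribution and identity link, with sites included as random effects to account for the clustering effect", so the interaction is a single term on the risk-difference scale. The Figure 2 entry in SAP Table 3 has the forest plot show each subgroup's absolute difference with its 95% confidence interval and the interaction p value.

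Both measures are held on their full scale. The Table 1 shell in the List of proposed inserts has a row "Body mass index, kg/m ²" as well as a separate row for 30 kg/m² or more, and it lists preoperative SpO2 in per cent.

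The table of modifications from the original plan records: "Added two additional subgroups: body mass index and duration of one-lung ventilation". The BMI split was therefore introduced in this SAP, while the SpO2 split was carried over from the published protocol. The section Other exploratory analyses deals with the components of the composite outcome, not with patient characteristics. No interaction with continuous BMI or SpO2 appears anywhere.

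**The concern.** A single cut treats BMI 18 and 29.9 as the same, and BMI 30 and 45 as the same. A change in the PEEP effect within either group adds nothing to the test. If the effect varies smoothly with body size or baseline oxygenation, the interaction p value in Figure 2 will miss it more often than a test on the values already recorded. That p value is the plan's only formal test of whether these two characteristics modify the effect.

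**Working it through.** **The plan's own figures.** Inputs from SAP Sample size and Table 2: "expected incidence of postoperative pulmonary complications of 23% and 17.25% in the lower and higher positive end-expiratory pressure groups", two-sided alpha 0.05, power 0.90, 1:1 allocation, five looks. For a fixed design with pooled null variance (mean risk 0.20125), n per arm = [1.960 × √(2 × 0.20125 × 0.79875) + 1.2816 × √(0.23 × 0.77 + 0.1725 × 0.8275)]² / 0.0575² = 1020, or 2040 in total. With the Table 2 boundaries at N = 2259, simulation gives total power of 0.90 and two-sided type I error of 0.050 with futility ignored. 2259 / 0.95 = 2378. The stated sizes reproduce, and 2259 is used as N below. The SAP states no power for any interaction.

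**Information kept by a split.** If the effect is linear in a covariate X, the efficiency of the split test relative to the linear test is the squared correlation of X with its two-group indicator. For normal X with share p beyond a cut at standardised value c, this is E = φ(c)² / [p(1 − p)]. With p = 0.20, c = 0.842 and φ(c) = 0.280, so E = 0.0784 / 0.16 = 0.49. The distributions are assumptions, because the SAP gives none:

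| Assumed distribution | Share beyond cut | E |
|---|---|---|
| Normal | 10 / 20 / 30 / 50% | 0.34 / 0.49 / 0.58 / 0.64 |
| Skewed BMI, mean 25-28, SD 4-5.5 | 11-33% at 30 or more | 0.43-0.63 |
| Whole-number, left-skewed SpO2, mean 96-98, SD 1.2-2 | 4-34% below 96% | 0.34-0.65 |

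Power of the split is Φ[(1.960 + z) × √E − 1.960], where z is the normal quantile of the power on the full scale. Over E = 0.34 to 0.65, 80% on the full scale becomes about 37-62% with the split.

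**Power for a given gradient.** Average outcome variance = (0.23 × 0.77 + 0.1725 × 0.8275) / 2 = 0.160. The standard error of the interaction per SD is √(4 × 0.160 / 2259) = 0.0168.

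- 4 points per SD: 0.04 / 0.0168 = 2.38. Full-scale power is Φ(2.38 − 1.96) = 66%. With the split, E = 0.43 gives Φ(2.38 × 0.656 − 1.96) = 34%, and E = 0.65 gives Φ(2.38 × 0.806 − 1.96) = 48%.
- 2 points per SD: 0.02 / 0.0168 = 1.19. Full-scale power is 22%; the split has 12% to 16%.
- 1 point per SD: full-scale power is about 9%.

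**Simulation.** Trials of 2259 patients were analysed with linear-probability regression and robust standard errors, without a site effect. Interaction tests were two-sided at 0.05, which is an assumption.

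| Gradient | Full scale | Split |
|---|---|---|
| BMI, 4 points per SD | 65-71% | 33-49% |
| SpO2, 4 points per SD | 63-65% | 43-50% |
| Either, 2 points per SD | about 22-24% | 11-16% |

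With no interaction, both tests reject in about 5% of trials. The formula and the simulation agree.

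**The opposite case.** If the effect is a step exactly at the cut, the split wins. With a 12-point step at BMI 30 (mean 26, SD 4.5, 18% at 30 or more), power was 85% with the split and 54% with the linear term. Over the step scenarios tried, the lead was 14 to 37 points.

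**The case against.** The strongest reply is that the plan contains no error. The cuts are named in advance, heterogeneity is judged by a proper interaction term rather than by separate p values within groups, and the primary test, its alpha and the sample size do not depend on this. That stands, and it limits the weight of the point.

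The size of the gain also needs care. Around a mean effect of −5.75 points, 4 points per SD means −5.75 − 8 = −13.75 at 2 SD on one side and −5.75 + 8 = +2.25 on the other, which is a change of sign. Nothing in the SAP suggests so strong a gradient. For weaker ones the full-scale test also usually misses it. This stands too.

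A third objection is practical. A linear covariate with an identity link can push fitted risks outside 0-1, which a two-group term does not do in its fixed part. In simulation at 4 points per SD, this happened in about half of trials when benefit grows with BMI, and in 64% when benefit grows as SpO2 falls. It was uncommon in the opposite directions (0-18% over the gradients tried). An added test therefore needs a stated fallback.

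A reader might infer three stronger points that the SAP does not support.

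- That the cuts lack any reason. The SpO2 cut comes from the published protocol, which is not at hand and may justify it.
- That a non-significant interaction will be reported as a consistent effect. The SAP does not say so, and its forest plot shows estimates with confidence intervals.
- That a linear test should replace the split. It would exchange one assumed shape for another, would do worse for a step, and could miss a U-shape.

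**Conclusion.** The point holds as an inexpensive improvement to a subgroup analysis. For BMI and baseline SpO2 the plan tests effect modification only on a single cut, although the full values are collected. Under a graded effect the split uses about one third to two thirds of the available information. At 4 points per SD this is about 33-50% power against 63-71%; at 2 points per SD or less neither test is adequate. With a very lopsided split (E = 0.34) the formula puts the cut lower still at 4 points per SD: Φ(2.38 × 0.583 − 1.96) = 28%.

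The direction of the loss follows from linearity alone. Its size rests on the assumed covariate distributions, a linear gradient, a two-sided 0.05 level for interaction, and a working model without site effects. The conclusion does not extend to duration of one-lung ventilation, which is also cut (at 120 minutes) but is measured after randomisation.

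**What to change.** In the SAP's Subgroup analysis section, add for BMI and baseline SpO2:

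*Heterogeneity will also be tested by a treatment-by-covariate term with the covariate as recorded (linear), fitted in the primary model on the risk-difference scale. If that model does not converge or gives fitted risks outside 0-1, a linear-probability model with robust standard errors clustered by site will be used. The estimated absolute difference will be plotted over the observed range of the covariate.*

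Keep the two-group estimates and their interaction p values in the forest plot, and report both tests for each variable without making either one decisive.

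The cost is a short addition to the text and two further model fits, plus the fallback where needed, on data already collected. The downsides are two more exploratory tests and a linear term that has less power than the cut if the effect is an abrupt step at exactly 30 kg/m² or 96%. The addition should be made before the data are unblinded, since the same analysis added later would be post hoc.
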